6.2.2 Experimental data analysis

All experimental methods carried out during this study will be conducted at the University of Liverpool by the study's designated research assistant. All experimental data generated will be processed and analysed using University equipment and any appropriate commercially available software as deemed necessary by the study's PI. All experimental data generated will be stored on computers and hardware owned by the University of Liverpool and will be directly accessible to the study's PI and research assistant for analysis and interpretation. No personal identifiers belonging to any participant will be kept at the University of Liverpool.

6.2.2.1 Cell lines

All cell lines used in this study will be generated from somatic patient cells. The cells used for reprogramming will be PBMCs isolated and cultured from whole blood. Cells will be reprogrammed using either Sendai-virus transduction or by electroporation of episomal plasmid vectors. Cell lines

Version 2.24. Date: 1547/095/2022; IRAS:

Page 29 of 44

generated will be allocated a pseudoanonymised form of identification by the research staff at the University of Liverpool. Surplus primary material (PBMC) will be cryopreserved in cryopreservation medium. Cells will be frozen in isopropanol containers at -80°C for 24 hours before being transferred to long-term storage at -150°C under HTA guidelines. All samples will be stored at the University of Liverpool.

6.2.2.2 Cellular Reprogramming

Sendai lines will be transduced with the CytoTune iPSC Sendai Reprogramming Kit (Invitrogen), which contains F-gene deficient Sendai-virus expressing the four Yamanaka transcription factors (SOX2 OCT3/4 c-MYC and KLF4). The reprogramming will be conducted according to manufacturer's instructions. After transduction, the Sendai-lines will be re-plated onto cell-free matrix-coated 6-well plates and cultured until iPSC colonies are ready to differentiate.

Electroporation lines will be transfected with integration free, episomal plasmid vectors containing pluripotency genes I-MYC, OCT3/4, SOX2 and KLF4 using a Nucleofector system (Lonza) according to the manufacturer's instructions. Transfected cells will be cultured under the appropriate culture conditions and then re-plated onto cell-free matrix-coated 6-well plates and cultured until iPSC colonies are ready to differentiate.

Throughout the reprogramming and cell maintenance period, we will cryopreserve stocks of iPSC lines in cryopreservation medium. Cell lines will be frozen in isopropanol containers at -80°C for 24 hours before being transferred for storage at -150°C at the University of Liverpool.

6.2.2.3 Microscopy

Brightfield microscopy will be used to analyse cellular reprogramming and differentiation efficiency as well as to assess the regular progress and overall health of the cells whilst in culture. Reprogramming efficiency will be assessed by microscopy in two ways – firstly, following transduction/transfection, all newly generated iPSC colonies will be counted and divided by the number of input cells used for reprogramming. Secondly, the number of iPSC colonies that survive following picking will be divided by the number of colonies that are selected for picking. The cardiomyocyte differentiation efficiency will be determined by dividing the number of observed beating areas by the total number of iPSC colonies that are used for differentiation.

Overall cell health will be assessed through regularly examining the morphology of the cells. Reprogrammed iPSC colonies will be examined for typical features indicative of good health such as dense, flat, rounded colony formation with even colouring and a high nucleus-to-cytoplasm ratio.

Microscope data on cell morphology, reprogramming efficiency and differentiation efficiency will be collected using and Invitrogen EVOS XL Core imaging system and analysed using an appropriate imaging software programme.

6.2.2.4 Polymerase Chain Reaction (PCR)

We will use PCR to characterise the gene expression of iPSC and cardiomyocyte cell lines. PCR data will be generated using several established techniques. Standard PCR and RT-PCR will be used to confirm the absence of exogenic genetic material from electroporated and Sendai-virus iPSC lines, respectively. The expression of EBNA-1, which will be present in the transfection plasmids, will be

Version 2.24. Date: 1547/095/2022; IRAS:

Page 30 of 44

assessed for electroporated lines. For Sendai-virus lines, the four viral transgenes (KLF-4, SOX-2, c-MYC and OCT-3/4) will be assessed. After verifying the absence of exogenic genetic material, the expression of endogenic pluripotency genes will be studied at the mRNA level by RT-PCR. GAPDH will be used as an endogenic control. Nucleic acid samples will be collected using commercially available reagents and collected samples will be stored at -80°C until extraction. Nucleic acid extraction will be performed using a commercially available extraction kit according to the manufacturer's instructions. Sample concentration will be transcribed into cDNA using a commercially available kit according to manufacturer's instructions and synthesised cDNA will be stored at -80°C until ready for use. PCR products will be separated and analysed using agarose gel electrophoresis and the results viewed using a UV gel documentation system. The data images will be further interpreted using an appropriate imaging software programme.

To obtain quantitative PCR data which will allow us to compare the expression of pluripotency genes both within the same subject and between individual subjects, we will use a fluorescent reporter probe-based qPCR method. cDNA samples will be synthesised as described above from cell lines at two different passages (early and late) and studied to detect the expression levels of endogenous pluripotency genes with GAPDH levels used as an endogenic control. Samples will be processed in triplicate and analysed using the double-delta ct method to calculate relative expression. Statistical analyses will be performed to study (1) the differences in relative gene expression at early and late passages in the same subject (Mann-Whitney U test) and, (2) significant differences between subjects at the same passage number (Kruskal-Wallis test). Statistical analysis will be conducted using the R computational software environment.

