3.3 OUTCOME

Our primary outcome for this study is to generate iPSC-derived cardiomyocytes that are reproducible, amenable to experimental analysis, and that recapitulate the phenotype of the donor at the molecular and cellular level. This will not only allow us to begin addressing the research questions set out in this study of being able to better understand chemotherapy-induced cardiotoxicity, but will also enable us to use the technology to investigate other cardiac conditions and congenital defects.

Secondary outcomes include:

- Identifying a doxorubicin-specific signature in the cells derived from our cardiotoxicity subjects
 which signifies a distinct biological process that is absent in the control group. This would allow us
 a potentially significant insight into the mechanistic effects of doxorubicin-induced cardiotoxicity
 at a cellular and molecular level.
- Identifying candidate biomarkers that are of a functional relevance to doxorubicin-induced cardiotoxicity. Novel biomarker discovery could potentially offer an enhanced alternative to the current standard of risk stratification and cardiotoxicity detection in the clinic.
- Obtaining data that will support further investigations into different areas of future research such as the role of candidate biomarkers that could predict anthracycline-induced cardiotoxicity in other cancers and what their relationships are to cumulative drug dosing strategies for example.

These outcomes could eventually enable clinicians to better predict which patients will develop cardiotoxicity and how their care can be more appropriately managed. The research will deepen the understanding of doxorubicin-induced cardiotoxicity for health care professionals and service providers for integrated care. It will also assist in providing a better understanding of the options available for supporting chemotherapy patients at various stages of their care both during and following the completion of their treatment. It has the potential to improve the wellbeing and lives of patients as well as to improve how primary and secondary care services work together. The study will develop high quality data that will be disseminated with researchers, service users and health care professionals to create more effective practices in care.

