3.6 SAMPLING

3.6.1 Size of sample

The maximum sample size for this pilot study at this stage will be 12 participants in total across all experimental groups (Figure 1). When selecting a sample size for this study we considered several factors including the nature of the study (i.e. a pilot study) and the financial feasibility of achieving our research aims at this stage. As this is a pilot study, we want to generate preliminary data that can support further funding applications that build on scientific evidence and eventually allow for larger sample sizes whilst still working realistically within the constraints of the study. Our approach is therefore to focus our efforts on obtaining a carefully planned smaller sample size which adequately represents significant aspects of the wider study population. This sample size is large enough to sufficiently address the primary research aims at the current stage and will provide valuable preliminary data to plan larger subsequent studies which will further address the overarching research questions.

Version 2.21. Date: 1517/095/2022; IRAS:

Page 23 of 44

Formatted: Indent: Left: 0.35 cm

[figure not shown]

Figure 1. Cancer patients with early-onset chronic cardiotoxicity and late-onset chronic cardiotoxicity will be recruited. Non-cardiotoxic patients will be matched to the cardiotoxic patients on tumour type, treatment regime and approximate age. For late-onset chronic cardiotoxic patients, noncardiotoxic patients will be recruited who have previously received the same treatment regime and not developed cardiotoxicity at the same point.

Version 2.21. Date: 1517/095/2022; IRAS:

Page 24 of 44

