6.2.2.6 Immunocytochemistry

We will use indirect immunocytochemistry (ICC) to characterise iPSC and cardiomyocyte cell lines at the protein level. This method will allow us to generate data that will confirm the simultaneous expression and cellular location of key pluripotent stem cell markers and cardiac-specific markers such as Troponin-T. The stained cells will be viewed using a fluorescence microscope and the images will be captured using a digital camera. Captured images will be interpreted and analysed with the aid of an appropriate imaging software, such as Adobe Photoshop, and data may be manipulated to include the addition of scale bars, contrast adjustment and image overlays. Data manipulation will not affect the result of the experiments in any way. Our interpretations of the data will be validated with the use of positive and negative staining controls and imaging parameters for the controls will be the same as those applied to the test dataset. In addition to obtaining data on protein expression levels, the cardiomyocyte differentiation efficiency will also be assessed by ICC. A select number of images (<5) will be captured at random and the number of cardiac TroponinT- positive cells will be divided by the total cell count. Cells will be counterstained with a nucleic acid stain (DAPI) to achieve this.

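### Quantitative PCR is normalised to GAPDH alone, with no stated stability check, so a GAPDH shift between lines or cell passages would look like a common change in every pluripotency gene

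*Protocol*

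**What the plan says.** Protocol section 6.2.2.4 uses PCR in two ways. For gel-based RT-PCR of the endogenous pluripotency genes, "GAPDH will be used as an endogenic control". For the probe-based quantitative assay, cDNA from an early and a late cell passage is again "studied to detect the expression levels of endogenous pluripotency genes with GAPDH levels used as an endogenic control". The calculation is fixed as well: "Samples will be processed in triplicate and analysed using the double-delta ct method to calculate relative expression".

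Two comparisons follow. The first is "the differences in relative gene expression at early and late passages in the same subject (Mann-Whitney U test"). The second is "significant differences between subjects at the same passage number (Kruskal-Wallis test"). Section 3.6.1 sets the number of donors: "The maximum sample size for this pilot study at this stage will be 12 participants in total across all experimental groups".

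GAPDH is the only reference gene named. The section describes no check that it is constant across lines or passages, and does not clearly say that the amount of RNA or cDNA entering each reaction is equalised.

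**The concern.** A relative-expression result is only as stable as its denominator. With one reference gene, any difference in GAPDH between two samples passes unchanged, on the log2 scale, into every pluripotency gene measured. Adding target genes or replicates does not help, because all of them share that denominator.

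The artefact also resembles the signal of interest. A line losing pluripotency could be expected to show its pluripotency genes moving together, and a GAPDH shift produces the same picture. A sound line could look unstable, or a real decline could be masked.

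The qPCR is the only analysis in the Protocol stated to compare lines at early and late passage. It therefore contributes to the case that the lines are of dependable quality. That lies upstream of the primary outcome in section 3.3, which is to "generate iPSC-derived cardiomyocytes that are reproducible, amenable to experimental analysis".

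**Working it through.** **Inputs from the Protocol.** One reference gene (GAPDH), double-delta Ct, triplicate processing, Mann-Whitney within subject and Kruskal-Wallis between subjects (6.2.2.4); at most 12 participants (3.6.1). No alpha, power or variance is stated for the PCR analysis, so there is no planned figure to reproduce.

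**Assumptions, not in the Protocol.** Between-line SD of GAPDH, s = 0.3 to 1.0 Ct. For the simulation in step 4: one line per subject, technical SD of 0.15 cycles per Ct, the triplicates treated as the observations in each group, and significance at p < 0.05.

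**Step 1: how a shift propagates.** Fold = 2^-(ddCt), where ddCt = (Ct_target - Ct_GAPDH)_late - (Ct_target - Ct_GAPDH)_early. Leave the target unchanged and let the GAPDH Ct rise by d. Then ddCt = -d and the apparent fold is 2^d, the same for every gene.

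| GAPDH shift d (cycles) | Apparent fold, every gene | Opposite direction |
|---|---|---|
| 0.25 | 1.19 | 0.84 |
| 0.5 | 1.41 | 0.71 |
| 1 | 2.00 | 0.50 |
| 2 | 4.00 | 0.25 |

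**Step 2: how often two lines would differ more than two-fold with no true difference.** The spurious difference between two lines is N(0, 2s²), and two-fold is 1 cycle, so P = 2 × [1 - Φ(1 / (√2 × s))]. For s = 0.5, √2 × 0.5 = 0.707, 1/0.707 = 1.414 and P = 16%. With the mean of three independent, equally stable references, replace s by s/√3. For s = 0.5 this gives 0.289, then √2 × 0.289 = 0.408, 1/0.408 = 2.449 and P = 1%.

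| s (Ct) | GAPDH alone | Mean of three references |
|---|---|---|
| 0.3 | 2% | <0.1% |
| 0.5 | 16% | 1% |
| 0.8 | 38% | 13% |
| 1.0 | 48% | 22% |

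The 95% limit of the spurious fold, 2^(1.96 × √2 × s), runs from 1.8 (s = 0.3) to 6.8 (s = 1.0) with GAPDH alone. With three references it runs from 1.4 to 3.0.

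**Step 3: one reference drifts and the others hold.** Averaging the Ct of k references turns a 1-cycle GAPDH shift into a fold of 2^(1/k): 2.00 for k = 1, 1.41 for k = 2, 1.26 for k = 3.

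**Step 4: effect on the planned tests.**

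- Kruskal-Wallis, 12 lines × 3 replicates, 3,000 simulated runs, no true target difference. It rejected in 1.5% of runs with s = 0, 13% with s = 0.1, 81% with s = 0.25 and 99.7% with s = 0.5.
- Mann-Whitney on one triplicate per passage. The smallest exact two-sided p is 2/C(6,3) = 2/20 = 0.10. A GAPDH shift would distort the fold estimate but could not produce p < 0.05.

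**The case against.** The strongest reply is that this argues from silence. The Protocol does not say that GAPDH will go unchecked, and reference-gene validation is assay detail that a laboratory procedure or analysis plan may hold. That is fair as to the missing check. It does not reach the normaliser, since section 6.2.2.4 itself fixes the reference gene, the calculation and the comparisons.

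A reader might infer several stronger things that the document does not support:

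- **That a GAPDH shift could never be noticed.** GAPDH Ct is measured in each sample, so drift could show in the raw values if input is equal. A shift of the same size and direction in all genes would also be a warning sign. What stands is that the normalised values alone cannot tell the artefact from a true common change.
- **That this is the plan's only quantitative check on the lines.** That holds only for the early-versus-late comparison. Section 6.2.2.3 quantifies reprogramming and differentiation efficiency, and section 6.2.2.6 states "We will use indirect immunocytochemistry (ICC) to characterise iPSC and cardiomyocyte cell lines at the protein level", with a count of troponin-positive cells. None of these uses GAPDH. Section 1.3 also says that no single method suffices to establish iPSC quality.
- **That the case-control results or the primary outcome are compromised.** Section 6.2.2.4 plans no cohort comparison by qPCR. The mass spectrometry (6.2.2.7) and electrophysiology (6.2.2.8) do not use GAPDH normalisation. The primary outcome concerns cardiomyocytes, whereas this assay measures pluripotency genes.
- **That GAPDH is known to vary here because the study examines energy metabolism.** The ATP and mitochondrial read-outs do not show that GAPDH differs between undifferentiated lines.

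Two further objections stand. The assumed SD range gives anything from 2% to 48%, so it shows sensitivity and not likelihood. And three references do not cure the problem: at s = 0.5 the effective SD is still about 0.29, a little above the 0.25 at which the simulated Kruskal-Wallis test rejected in 81% of runs.

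**Conclusion.** The point holds in a limited form. Relying on one reference gene with no stated stability check leaves the two planned qPCR comparisons open to an artefact of 2^d-fold in every gene. That relation follows exactly from the stated method. Its frequency does not: the range of 2% to 48% of line pairs spuriously beyond two-fold rests on an assumed between-line SD of 0.3 to 1.0 Ct, and the improved range of under 0.1% to 22% further assumes that the three references are independent and equally stable, which is a favourable case. Within a subject the harm falls on the fold estimate, since on one triplicate per passage the planned test cannot reach 0.05.

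Nothing in the Protocol is contradicted and no stated figure is wrong. This is a minor, inexpensive improvement to a stated method and does not threaten the study's main comparisons.

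**What to change.** In section 6.2.2.4, replace GAPDH as sole qPCR control by the mean Ct of GAPDH and two further prespecified reference genes from different pathways, run on the same cDNA with equal input. Report the Ct of each reference gene by cell passage and by subject, so that drift can be seen.

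If a reference may be excluded for drift, set the threshold in advance and report results with and without it. An open-ended rule would add analyst discretion, and two references drifting together could lead to the sound one being removed.

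The cost is two more probe assays per cDNA sample, more wells per plate and a few sentences of text. No extra patients, blood or cells are needed. The change reduces the reference-gene artefact but does not remove it, so a uniform shift across all pluripotency genes should still be read against the raw reference Ct values and the immunocytochemistry.

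### Both qPCR tests take the triplicate runs as the sample: the per-subject early-versus-late test cannot go below an exact p of 0.10, and the between-subject test measures donors only against replicate noise

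*Protocol*

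**What the plan says.** Protocol section 6.2.2.4 describes a probe-based qPCR comparison of pluripotency genes, within and between subjects. The material is cDNA "from cell lines at two different passages (early and late"). On replication it says: "Samples will be processed in triplicate and analysed using the double-delta ct method to calculate relative expression".

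Two tests are then named. The first is "1) the differences in relative gene expression at early and late passages in the same subject (Mann-Whitney U test"). The second looks for "significant differences between subjects at the same passage number (Kruskal-Wallis test"). On software, the section adds: "Statistical analysis will be conducted using the R computational software environment".

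The section does not give the number of lines per subject, say whether the three values are averaged, name the unit of analysis or set a significance level.

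On the number of donors, section 3.6.1 states: "The maximum sample size for this pilot study at this stage will be 12 participants in total across all experimental groups (Figure 1"). The split between groups is in a figure that is not reproduced in the text at hand.

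**The concern.** A rank test needs independent observations of whatever it is meant to generalise over. Here the only repeated values within a subject and passage are the triplicate runs. Running one sample three times shows how precise the assay is. It does not show how far a line drifts between passages, or how far donors differ relative to line-to-line variation.

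The two tests then go wrong in different ways:

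- **Early versus late.** The per-subject test has too few values to give a small p, however large the change.
- **Between subjects.** The error term is replicate scatter, so the p-value answers a narrower question than a reader would expect.

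Reproducibility is part of the primary outcome in section 3.3, and section 2.1.1 lists PCR among the methods used to validate the lines. A column of non-significant early-versus-late results could be taken as proof of stability. Significant between-subject results could be taken as established biological differences, in data meant to support larger studies (section 3.6.1).

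**Working it through.** **Inputs.** From section 6.2.2.4: 3 values per sample, 2 passages, Mann-Whitney within subject, Kruskal-Wallis between subjects. From section 3.6.1: at most 12 donors. Assumed because not stated: one line per donor, a two-sided 5% level, and the ratio of between-donor SD to replicate SD. The plan gives no figure of its own to reproduce.

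**Step 1. Early versus late within one subject, 3 v 3.** The number of ways to divide six ranks is C(6,3) = 20.

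- Smallest exact two-sided p = 2/20 = 0.10.
- Smallest exact one-sided p = 1/20 = 0.05, which is still not below 0.05.
- Normal approximation at complete separation: the mean of U is 4.5 and its variance is 3 × 3 × 7/12 = 5.25. With continuity correction, z = 4.0/2.291 = 1.75 and p = 0.081. Without it, z = 4.5/2.291 = 1.96 and p = 0.0495.
- If all three values are tied within each passage, the corrected approximation gives 0.047.
- With 4 independent values per passage, the exact minimum would be 2/C(8,4) = 2/70 = 0.029.

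So with 3 v 3 the exact test cannot reach 5%. Only an uncorrected approximation or complete ties would take it just under, and the protocol plans neither.

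**Step 2. The same test pooled over subjects.** Each donor would supply both an early and a late value. Those values are paired, and Mann-Whitney assumes two independent samples.

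**Step 3. Kruskal-Wallis with one value per donor.** For 12 donors each forming its own group, the ranks are always 1 to 12 and the sum of squared ranks is 650. Then H = 12/(12 × 13) × 650 − 3 × 13 = 50 − 39 = 11 on 11 degrees of freedom, so p = 0.44 whatever the data. The test is informative only if the replicates count as observations.

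**Step 4. Kruskal-Wallis with three values per donor.** For k donors, N = 3k and H = 12/(N(N+1)) × Σ(Rᵢ²/3) − 3(N+1), where Rᵢ is the rank sum of donor i. At complete separation:

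- 3 donors: H = 7.20, p = 0.027
- 6 donors: H = 16.58, p = 0.005
- 12 donors: H = 34.78, p = 0.0003

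Share of simulated data sets with p < 0.05 (normal donor and replicate errors, 4,000 runs per cell):

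| Donor SD / replicate SD | 12 donors | 6 donors | 3 donors |
|---|---|---|---|
| 0 | 2% | 2% | 1% |
| 0.5 | 16% | 9% | 4% |
| 1 | 69% | 37% | 10% |
| 2 | 99% | 82% | 32% |
| 3 | 100% | 95% | 46% |

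**Step 5. After averaging to one value per donor and passage.** A signed-rank test of early minus late across n donors has a smallest two-sided p of 2/2ⁿ. That is 2/4096 = 0.0005 for 12 donors and 2/64 = 0.031 for 6. For 5 donors it is 2/32 = 0.0625, so at least 6 donors with both passages are needed to reach 5%.

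**The case against.** **One line per donor is not stated.** The section speaks of cell lines without a number, and never calls the triplicates technical. Section 6.2.2.3 has several colonies picked, sections 6.2.2.1 and 6.2.2.2 allow two reprogramming methods, and section 3.5.1 allows a second blood sample. Several independent lines per donor are therefore possible, and four values per passage would bring the minimum p to 0.029. This stands as a condition on the result. It does not remove the problem, because the text names both tests and describes no within-subject replication except the triplicate.

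**A reader might infer that Kruskal-Wallis will be significant for almost any set of donors.** The documents do not support that. They give no SDs, 12 is a maximum, and the table shows low rejection rates when donors differ little or are few. What holds is narrower: the p-value compares donor differences with replicate scatter alone.

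**A reader might also fault the tests for never comparing cases with controls.** That is not an error here. The stated purpose is to compare expression within and between individual subjects, as part of line characterisation under Aim 1. The comparison of cardiotoxicity with non-cardiotoxicity samples is planned for the proteomics in section 6.2.2.7.

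**Line quality does not rest on this p-value.** Section 1.3 says that no single method suffices, and the plan also uses morphology, transgene loss, karyotyping and immunocytochemistry. This stands, and it limits the importance of the point.

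**A paired test across donors answers a different question.** It estimates average drift, and drifts in opposite directions can cancel. This stands too, so each donor's own change must be shown beside the test.

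**Conclusion.** The point holds as wrong as written, with moderate importance. As section 6.2.2.4 is worded, replicates are the sample in both tests.

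- **Early versus late.** With one line per donor, the exact per-subject test has a floor of p = 0.10 and cannot reach a two-sided 5% level. A non-significant result must not be read as evidence of a stable line. Read as a pooled test, it ignores the pairing.
- **Between subjects.** A small p shows only that donors differ by more than replicate noise. How often it occurs depends on an SD ratio that the protocol does not give.

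The conclusion on the first test rests on one line per donor, three values per passage, the exact test and a two-sided 5% level. The documents state only the triplicate. The finding is therefore not that the early-versus-late comparison could never be significant under any arrangement of lines. It is that the arrangement described cannot deliver it.

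**What to change.** Amend section 6.2.2.4 as follows:

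1. State the number of lines per donor and name the unit of analysis. Average the triplicates to one delta-Ct per line and passage.
2. Test early minus late across donors with a paired test such as the Wilcoxon signed-rank, and list or plot each donor's own change.
3. Replace the between-subject Kruskal-Wallis p-value with a descriptive report of donor-to-donor spread. If independent lines per donor exist, use those as the replicates instead.
4. State that a non-significant early-versus-late result is not evidence of stability.

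The cost is a few sentences, with no new samples or assays. The downside is that there is no p-value for an individual subject and there will be fewer significant between-subject results. The paired test also needs at least 6 donors with both passages to be able to reach 5%.
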